1.3. Prior Human Experience

A Phase 1 study in 48 healthy volunteers has been completed. This is a randomized, double-blind, placebo-controlled, two-period study in which subjects received either CCX168 or placebo (3:1 ratio) as a single dose in Period 1 and as multiple once daily or twice daily doses in Period 2. Single doses of 1, 3, 10, 30, and 100 mg CCX168 were studied, 6 subjects in each dose cohort received CCX168 and 2 received placebo, except in cohort 1 in which 5 subjects received CCX168 and 3 received placebo. In Period 2, CCX168 doses of 1, 3, and 10 mg once daily for 7 days, and 30 and 50 mg twice daily for 7 days, were studied.

CCX168 appeared to be well tolerated by study subjects in this study. No serious adverse events or withdrawals due to adverse events have been observed. A summary of all the treatment-emergent adverse events observed in the single-dose period and the multi-dose period of the study is provided in the Investigator's Brochure.

All adverse events in the single-dose period were mild except for one AE of injection site phlebitis in the 3 mg CCX168 group and one of WBC count decrease in the 1 mg group that were considered moderate in intensity.

The most common AE reported in subjects receiving CCX168 in the multi-dose period was headache, reported in 21% of subjects receiving CCX168 compared to 18% in the placebo group. Diarrhoea (7% vs. 9% in placebo), dizziness (7% vs. 0% in placebo), lower abdominal pain (7% vs. 0% in placebo), nausea (7% vs. 0% in placebo), and oropharyngeal pain (7% vs. 9% in

placebo) were the other more commonly observed AEs. No clinically significant changes in laboratory parameters, vital signs, or ECG parameters were observed. In the multi-dose period of the study, a slight decrease in mean WBC and neutrophil count was observed in subjects receiving CCX168 compared to placebo. These WBC and neutrophil counts most often remained within the reference range, decreases were observed within 1 to 2 days after start of dosing, appeared to be most pronounced in subjects with baseline WBC and neutrophil counts at the higher end of the normal range, and did not appear to progressively worsen over the 7-day dosing period. These slight changes in WBC and neutrophil counts may be related to the pharmacology of CCX168 as a C5aR blocker.

No clinically significant changes in laboratory parameters, vital signs, or ECG parameters were observed. Key pharmacokinetic results (mean, SD) from the single-dose period and the multiple dose period of clinical trial CL001_168 are provided in the Investigator's Brochure.

Following a single dose of 1-100 mg, mean exposures as measured by $AUC_{0-\infty}$ ranged from 6.14 to 2030 ng•hr/mL while C_{max} ranged from 1.84 to 197 ng/mL. The apparent mean terminal half-life ranged from 1.92 to 71.8 hr, while clearance ranged from 51.7 to 195 L/hr.

Following administration at 1 to 10 mg CCX168 q.d. for 7 days, mean exposures as measured by $AUC_{0-\tau}$ ranged from 8.72 to 104 ng•hr/mL on Day 1 and from 11.2 to 178 ng•hr/mL on Day 7, while C_{max} ranged from 2.59 to 19.2 ng/mL on Day 1 and 2.86 to 31.4 ng/mL on Day 7.

Following b.i.d. administration at 30 to 50 mg, mean exposures as measured by $AUC_{0-\tau}$ ranged from 380 to 1400 ng•hr/mL on Day 1 and from 880 to 2340 ng•hr/mL on Day 7, while C_{max} ranged from 97.2 to 423 ng/mL on Day 1 and 161 to 425 ng/mL on Day 7.

CCX168 levels declined in a biphasic exponential manner, with a rapid distribution phase and an apparent mean plasma terminal $t_{1/2}$ ranging from 12.2 to 162 hr following once daily administration.

Repeat administration for seven days of CCX168 resulted in moderate accumulation (at 1 and 3 mg q.d.) or high accumulation (10 mg q.d. or 30 – 50 mg b.i.d.) of CCX168, consistent with the observed terminal half-life in these dosing groups. After q.d. dosing, the exposure of CCX168 as measured by C_{max} and AUC is approximately dose proportional in the 1 – 10 mg dose range. After b.i.d. dosing, the exposure increase of CCX168 statistically appears to be linearly proportional for 30 mg and 50 mg doses. Based on the measured trough concentrations, in general, CCX168 appeared to reach steady state after 3-4 days of dosing.

Food effect was also investigated by comparing the Day 7 0-12h (fasted) and 12-24h (fed) parameters. No significant effects were seen in either dose group.

CCX168-M1, a monohydroxylation metabolite of CCX168, was found to be a **significant** circulating metabolite in humans. Following 7 days of oral administration of CCX168 at 30 mg and 50 mg b.i.d., the AUC_{0-24} for CCX168-M1 was 1600 and 2340 ng•hr/mL, respectively. These values represent 85% and 52%, respectively, of the levels of CCX168 measured at those doses. Its exposure was adequately covered in rats and cynomolgus monkeys in the toxicology studies that support this Phase 2 clinical trial.

In study CL001_168, pharmacodynamics assays indicated that a dose of 30 mg CCX168 twice daily was highly effective in blocking C5a-mediated upregulation of CD11b on circulating leukocytes obtained from these subjects.

Clinical trial CL002_168 in patients with AAV is ongoing. This is a randomized, double-blind, placebo-controlled clinical trial being conducted in three sequential steps. A total of 26 subjects have been enrolled in the first two steps of this clinical trial. A summary of the safety and efficacy results, as well as the PK results from the first two steps are provided in the Investigator's Brochure.

Clinical trial CL003_168 in patients with AAV is being initiated in 2014. This is a randomized, double-blind, placebo-controlled trial in up to approximately 45 subjects.

1.4. Rationale for the Study

IgAN is reported as the most common glomerulonephritis worldwide. It is associated with a wide spectrum of disease severity and rate of progression of renal failure. The best well established risk factor of progressive loss of renal function from IgAN is the persistent presence of proteinuria > 1 g/day, with some studies suggesting that the persistence of even lower levels of proteinuria (> 500 mg/day) may be associated with worse prognosis. Other clinical and histologic factors have also been associated with a faster decline in renal function, although these are not as well documented.

Despite the relative high prevalence of disease worldwide, there is a paucity of evidence-based therapy available for the treatment of IgAN. Current guidelines include initiating therapy of patients with hypertension and persistent proteinuria > 1 g/day with renin-angiotensin-aldosterone system (RAAS) blockade with an ACE inhibitor or ARB to attain a level of proteinuria below that threshold.

For patients who fail to attain a reduction of proteinuria to < 1 g/day, it is currently “suggested” that patients be treated with a course of glucocorticoids ([KDIGO Clinical Practice Guideline for Glomerulonephritis, 2012](#)). However this “suggestion” carries an evidence-based grade of 2C, given the “weakness” of the data supporting the efficacy of such therapy in altering long term outcomes of patients. In addition, the use of glucocorticoids for several months (e.g., 6 months in the “Pozzi” protocol; [Pozzi et al., 1999](#)) is associated with significant risk of adverse effects especially in the adult population.

Therefore, patients with relatively modest degree of proteinuria and well preserved eGFR (or stable eGFR if the decline is attributable to other cause than IgAN) represent a large pool of patients with a perceived increased risk of GFR decline, but no established, safe and effective treatment.

This patient population is ideal for a pilot study of CCX168. Phase 2 study data in patients with ANCA-associated vasculitis suggest a significant anti-proteinuric effect of CCX168 in the majority of treated patients (mean decrease of approximately 60% in urinary ACR over 12 weeks of treatment with CCX168). This treatment effect was observed in patients receiving CCX168 plus glucocorticoids, but also in patients receiving CCX168 with no glucocorticoids.

For patients with IgAN who have already demonstrated a decline in eGFR, more aggressive therapy with corticosteroids is warranted, and a delay in such treatment for the duration of the pilot study with a medication of unproven efficacy would be inappropriate at this early stage of clinical development.

A dose regimen of 30 mg CCX168 given twice daily is being tested in study CL002_168 in AAV and showed promising efficacy and a good safety profile. This dose regimen has been selected for this clinical trial in patients with IgAN.

2. OBJECTIVES

2.1. Primary Objective

The primary safety objective of this study is to evaluate the safety and tolerability of CCX168 in subjects with IgAN on background supportive therapy with a maximally tolerated dose of RAAS blockade.

The primary efficacy objective is to evaluate the efficacy of CCX168 based on an improvement in proteinuria.

2.2. Secondary Objectives

The secondary objectives of this study include assessment of:

1. Change in albuminuria with CCX168 treatment;
2. Change in renal function based on eGFR with CCX168 treatment;
3. Change in hematuria with CCX168 treatment;
4. Change in renal inflammatory activity based on urinary monocyte chemoattractant protein-1 (MCP 1):creatinine ratio and urinary epidermal growth factor (EGF):MCP-1 ratio with CCX168 treatment;
5. Change in serum IgA:plasma C3 ratio with CCX168 treatment;
6. Changes in pharmacodynamic markers in plasma and urine with CCX168 treatment, e.g., C3a, C5a, properdin, and sC5b-9;
7. Evaluation of the pharmacokinetic profile of CCX168 in subjects with IgAN.

3. STUDY DESIGN

This is a pilot study to test the safety, tolerability, and efficacy of CCX168 in reducing proteinuria in patients with IgAN and persistent proteinuria despite supportive therapy with a maximally tolerated RAAS blocker.

Patients will be screened for enrolment based on biopsy proven IgAN, and documentation of proteinuria > 1 g/g creatinine (by first morning urinary protein:creatinine). The screening period will be up to 14 days. Screening procedures will include demographics, medical history, medication history, physical examination and vital signs, serum pregnancy test for women of childbearing potential, serum chemistry, hematology, urinalysis, viral screening, and estimated glomerular filtration rate (eGFR) assessment. To be eligible for study participation, a patient must have had a renal biopsy in the past 3 years confirming the diagnosis of IgAN. If not done, a renal biopsy needs to be done for eligibility assessment. Patients meeting inclusion and exclusion criteria will be enrolled for blood pressure/RAAS blockade titration and run-in period.

At screening, patients should ideally be on one or two RAAS blocker(s) and have BP <140/90 mmHg. Patients not on an RAAS blocker can be started, and have the medication dose adjusted to a maximally tolerated dose (MTD) within a period not to exceed 4 weeks.

MTD for RAAS blockade is defined as:

- a dose attaining a target blood pressure less than 125/75 mmHg, or
- the maximum recommended dose (according to the label of the RAAS blocker), or
- the maximum dose tolerated by the subject from a safety/tolerability perspective.

If the blood pressure target of <125/75 mmHg is not achieved during the titration period, additional anti-hypertension medication (non-ACE-I or ARBs) should be considered to achieve this blood pressure goal. All patients must participate in an 8-week run-in period during which they must be on a stable, MTD of an RAAS blocker before starting treatment with CCX168 on Day 1. If a patient is on two RAAS blockers (any combination of ACE inhibitor, ARB, and aldosterone blocker) at the time of screening, the patient must remain on stable doses of these medications throughout the 8-week run-in period. Titration to an MTD for both RAAS blockers is not needed in this case if the blood pressure goal has been achieved.

After the 8-week run-in period has been completed, two back-to-back first morning urine collections need to be obtained for protein and creatinine measurements. The geometric mean of the two urinary PCR measurements must be > 1 g/g creatinine for eligibility for further study participation.

On Day 1, patients meeting inclusion criteria will start CCX168 treatment. Patients will take CCX168 30 mg orally twice daily for 12 weeks (84 days). The CCX168 dose will be taken in the morning optimally within one hour after breakfast and in the evening optimally within one hour after dinner. After the 84-day treatment period, patients will be followed for 12 weeks (84 days) while continuing to take their RAAS blocker treatment at a stable dose.

At post-Day 1 study visits, blood and urine samples will be collected for safety, efficacy, and pharmacokinetic measurements. A serum pregnancy test for women of childbearing potential will be done on Days 29, 43, 57, 85, 113, and 169. Physical examinations and vital signs assessments will be performed throughout the study. Concomitant medication and adverse event assessments will be made at every study visit. An optional renal biopsy could be performed after the 12-week treatment period to assess the effect of CCX168 treatment on kidney histology.

During the 12-week treatment period and the 12-week follow-up period, the dose(s) of RAAS blocker(s) must remain unchanged. No new RAAS blocker or non-dihydropyridine calcium channel blocker or diuretic may be added during the study period (active treatment period or follow up).

During the treatment period with study medication and the 12 weeks of follow up thereafter, no new immunomodulatory medication may be started including, but not limited to cyclosporine, tacrolimus, mycophenolate mofetil, azathioprine, cyclophosphamide, or glucocorticoids (e.g. prednisone).

Concomitant use of omega-3 fatty acid supplements (e.g., fish oil) is permitted IF the medication is started at the time of, or before screening, and is maintained at a stable dose during the rest of the study until the end of the follow-up period (Day 169).

Patients will visit the study center on Days 1, 8, 15, 29, 43, 57, 85, 113, 141, and 169 for the treatment and follow-up period.

Duration of treatment with study medicine: 84 days

Duration of follow up after end of treatment with study medicine: 84 days

Subjects who experience a decrease in eGFR from baseline of $> 10 \text{ mL/min/1.73 m}^2$ or $> 20\%$ (confirmed by repeat after 2 weeks), which is otherwise not explained (e.g., dehydration, new medication), or an increase in proteinuria by $> 3 \text{ g/g}$ creatinine from baseline or to a level $> 8 \text{ g/g}$ (confirmed by repeat after 2 weeks) during the 12-week treatment period, will exit the treatment phase of the study and be treated at the discretion of their primary nephrologist. They will remain in the study for follow up and outcome recording.

The cumulative safety data from the study will be reviewed in near real time by the Sponsor's Medical Monitor.

Subjects will be discharged from the study when all the Study Day 169 visit procedures have been completed. The subject's condition will be evaluated by the Investigator at the end of the clinical trial (Day 169). Appropriate standard of care medical treatment will be implemented to all subjects as determined by their primary nephrologist.

To the extent possible, any adverse events that are deemed study drug-related and are ongoing at discharge will be followed-up to resolution or until a determination is made that the unresolved event is stable.

4. STUDY POPULATION

4.1. Size of the Population

Up to approximately 20 male or female subjects with IgAN will be enrolled in this study. Subjects who started the CCX168 treatment period and drop out prematurely will not be replaced. However, subjects who drop out during the titration and run-in periods may be replaced.

4.2. Inclusion Criteria

Subjects must meet all of the following inclusion criteria in order to enter the study:

1. Biopsy-proven IgAN performed for clinical purposes within 3 years prior to screening;
2. eGFR $> 60 \text{ mL/min/1.73 m}^2$ (by MDRD equation) OR eGFR $> 45 \text{ mL/min/1.73 m}^2$ if eGFR has not declined $> 10 \text{ mL/min/1.73 m}^2$ over the previous 24 weeks;
3. Proteinuria, defined as first morning urinary PCR $> 1 \text{ g/g}$ creatinine;
4. Male or female subjects, aged at least 18 years; Where allowed by local regulations, female subjects of childbearing potential may participate if adequate contraception is used during, and for at least the three months after study completion; Male subjects with partners of childbearing potential may participate in the study if they had a vasectomy at least 6 months prior to randomization or if adequate contraception is used during, and for at least the three months after study completion; Adequate contraception is defined as resulting in a failure

rate of less than 1% per year (combined estrogen and progestogen [oral, intravaginal, or transdermal], or progestogen-only hormonal contraception (oral, injectable, or implantable), intra-uterine device, intra-uterine hormone releasing system, bilateral tubal occlusion, vasectomized partner, or sexual abstinence);

5. Willing and able to give written Informed Consent and to comply with the requirements of the study protocol; and
6. Judged to be otherwise healthy by the Investigator, based on medical history, physical examination, and clinical laboratory assessments. Subjects with clinical laboratory values that are outside of normal limits (other than those specified in the Exclusion Criteria) and/or with other abnormal clinical findings that are judged by the Investigator not to be of clinical significance, may be entered into the study.

4.3. Exclusion Criteria

1. Severe renal disease as determined by rapid decline in eGFR (defined as >10 mL/min/1.73 m² over 24 weeks prior to screening, not otherwise explained);
2. Pregnant or nursing;
3. Proteinuria > 8 g/day (or >8 g/g creatinine);
4. Patients with systemic manifestations of Henoch-Schönlein purpura within the last 2 years prior to screening;
5. Patients with IgAN deemed secondary to underlying disease: e.g., diabetes, liver disease, cirrhosis, celiac disease, HIV, inflammatory bowel disease, lymphoma, or associated with any other multi-system autoimmune disease;
6. Biopsy report demonstrating severe crescentic IgAN ($>25\%$ crescents), OR $>50\%$ interstitial fibrosis and/or tubular atrophy ("T2") ([Cattran et al. 2009](#)), OR a high likelihood of rapid decline in eGFR based on an MEST ("Oxford") classification (M = mesangial hypercellularity; E = endocapillary proliferation; S = segmental glomerulosclerosis/adhesion; T = tubular atrophy/interstitial fibrosis) score of M1, E0, T1, or M0/1, E1, T1 ([Cattran et al. 2009](#));
7. History of treatment with glucocorticoids, cyclophosphamide, azathioprine, mycophenolate mofetil, or any biologic immunomodulatory agent within the 24 weeks prior to screening;
8. Symptomatic congestive heart failure requiring prescription medication, clinically evident peripheral edema of cardiac origin, poorly-controlled hypertension (systolic blood pressure >160 or diastolic blood pressure >95), history of unstable angina, myocardial infarction or stroke within 6 months prior to screening;
9. History or presence of any form of cancer within the 5 years prior to screening, with the exception of excised basal cell or squamous cell carcinoma of the skin, or cervical carcinoma in situ or breast carcinoma in situ that has been excised or resected completely and is without evidence of local recurrence or metastasis;
10. Positive HBV, HCV, or HIV viral screening test;
11. History of tuberculosis;

12. Any infection requiring antibiotic treatment that has not cleared prior to starting CCX168 treatment on Day 1;
13. WBC count less than 4000/ μ L, or neutrophil count less than 2000/ μ L, or lymphocyte count less than 1000/ μ L;
14. Hemoglobin less than 9 g/dL (or 5.56 mmol/L) at screening;
15. Evidence of hepatic disease; AST, ALT, alkaline phosphatase, or bilirubin $>$ 3 x the upper limit of normal;
16. Participated in any clinical study of an investigational product within 30 days prior to screening or within 5 half-lives after taking the last dose; and
17. History or presence of any medical condition or disease which, in the opinion of the Investigator, may place the subject at unacceptable risk for study participation.

4.4. Removal of Subjects from Therapy or Assessment

Subjects may be terminated early from the study for any of the following reasons:

1. Subject request: Subjects may withdraw their consent to participate in the study at any time without prejudice.
2. Investigator request: The Investigator may withdraw a subject if, in his/her clinical judgment, it is in the best interest of the subject or if the subject cannot comply with the protocol.
3. Sponsor request.

In the event of withdrawal from the study prior to the Day 85 visit, the tests and evaluations listed for Study Day 85 should be carried out as part of the Early Termination visit, whenever possible. For subjects who withdraw after Day 85, the Day 169 study procedures should be performed. The Sponsor should be notified of all study withdrawals in a timely manner.

Subjects who experience a decrease from baseline in eGFR $>$ 10 mL/min/1.73 m² or $>$ 20%, (confirmed by repeat after 2 weeks) which is otherwise not explained (e.g., dehydration, new medication), or an increase in proteinuria of $>$ 3 g/g creatinine from baseline or to a level $>$ 8 g/g (confirmed by repeat after 2 weeks) during the 12-week treatment period, will exit the treatment phase of the study and be treated at the discretion of their primary nephrologist. They will remain in the study for follow up and outcome recording.

In the event of treatment failure where rescue treatment such as corticosteroid therapy is needed, the study drug (CCX168) will be discontinued, and appropriate SOC measures will be taken. However, the subject will be asked to remain in the study and complete all remaining study visits. If this is not possible, an attempt will be made to complete all procedures scheduled for the Day 85 visit (if the rescue event occurred prior to the Day 85 visit) and Day 169 (if the rescue event occurred after the Day 85 visit).

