 AUC_{0-6} Area under the plasma concentration-time curve from Time 0 to Hour 6 on Day 1
 C_{min} Trough level plasma concentrations at post-Day 1 visits

The relationship between PK parameters and renal function based on eGFR will be evaluated. The data may also be used to evaluate the PK/PD relationship of CCX168 treatment. To this end, the change and/or percent change from baseline in urinary ACR, PCR, eGFR, urinary MCP-1:creatinine ratio, and other biomarkers may be used as PD markers.

STUDY SCHEMA

TIME AND EVENTS TABLE

	Screening ²	Titrat- ion	Study Day ¹												
			Run-in			Treatment						Follow-up			
			-63	-35	-7 to -2 ³	1 ⁴	8	15	29	43	57	85	113	141	169
Informed consent	X														
Demographics, medical history, prior medications	X														
Physical examination ⁵	X					X ⁶			X	X	X	X	X	X	X
Blood pressure ⁷	X	X	X	X	X, X	X ⁶	X	X	X	X	X	X	X	X	X
RAAS blocker dose titration ⁸		(X)													
RAAS blocker stable dosing at MTD			X→	→	→	→	→	→	→	→	→	→	→	→	→
Other vital signs ⁹	X					X ⁶	X	X	X	X	X	X	X	X	X
Serum pregnancy test for women of childbearing potential	X				X				X	X	X	X	X		X
HIV, HBV, HCV testing	X														
Serum chemistry ¹⁰ , hematology	X					X ⁶	X	X	X	X	X	X	X	X	X
Serum creatinine (not full chemistry)			X	X	X										
Urinalysis ¹¹	X					X ⁶	X	X	X	X	X	X	X	X	X
Urine protein and creatinine assays	X		X	X	X, X	X ⁶	X	X	X		X	X	X	X	X
Renal biopsy ¹²	X											X			
Urine albumin, MCP-1, EGF, and microscopic RBC count			X	X	X	X ⁶	X	X	X		X	X	X	X	X
Serum IgA and plasma C3 samples						X ⁶			X		X	X	X	X	X
CCX168 dispensing						X ⁶	X	X	X	X	X				
CCX168 dosing 30 mg b.i.d.						X→	→	→	→	→	→	→X			

	Screening ²	Titrat- ion	Study Day ¹												
			Run-in			Treatment						Follow-up			
	≤ 14 days	≤ 28 days	-63	-35	-7 to -2 ³	1 ⁴	8	15	29	43	57	85	113	141	169
CCX168 accountability							X	X	X	X	X	X			
PD plasma sample collection ¹³						X ⁶	X	X	X		X	X	X	X	X
PD urine sample collection						X ⁶	X	X	X		X	X	X	X	X
PK plasma sample collection ¹⁴						X	X	X	X	X	X	X			
Concomitant medications	X	X	X	X	X, X	X	X	X	X	X	X	X	X	X	X
Adverse event assessment		X	X	X	X, X	X	X	X	X	X	X	X	X	X	X

¹ Visit Days 1, 8, and 15 must occur on the scheduled study days. Visit Days 29, 43, 57, and 85 may occur within a +/- 2-day window of the scheduled visit.

Visit Days 113, 141, and 169 may occur within a +/- 4-day window of the scheduled visit.

² Screening must occur within a period not to exceed 14 days.

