- The subject will be asked to take the dose of study medication, 3 x 10 mg CCX168 capsules, while at the study center, unless the medication has already been taken that morning; the time of dosing will be recorded;
- All adverse events will be recorded;
- After all study procedures have been completed, the subject will be reminded to:
 - Come to the study center for the Day 15 study visit with their first morning urine sample;
 - Store the study medications in a cool and dry place according to label instructions for the duration of the study;
 - Take the CCX168 medication every morning and evening, approximately 12 hours after the morning dose;
 - Not to take CCX168 medication on the morning of Day 15, unless the visit is scheduled in the afternoon, in which case CCX168 medication should be taken the morning of Day 15; and
 - Continue taking their RAAS blocker(s) at a stable dose, and all their other concomitant medications as usual.

6.6. Study Day 15

The Study Day 15 visit must occur on the scheduled date. During this visit, the following study procedures will be performed:

- Vital signs (temperature, blood pressure, heart rate) will be measured supine after at least 3 minutes of rest;
- Serum chemistry and hematology; an eGFR will be calculated;
- Urinalysis, including pH, specific gravity, glucose, nitrite, ketones, bilirubin, urobilinogen, RBCs, and WBCs on a first morning urine sample collection;
- Urinary protein, creatinine, albumin, MCP-1, EGF, and microscopic RBC count on a first morning urine sample collection;
- Plasma samples will be collected for PD marker and PK assessment; the time of sample collection as well as the date and time of the last dose of CCX168 prior to sample collection will be recorded;
- A urine sample will be collected for PD marker assessment;
- Any changes in concomitant medication use will be recorded;
- Study drug accountability will be performed on all returned study medication;
- Four bottles of CCX168 study medication will be dispensed to the subject, with dosing instructions;

- The subject will be asked to take the dose of study medication, 3 x 10 mg CCX168 capsules, while at the study center, unless the medication has already been taken that morning; the time of dosing will be recorded;
- All adverse events will be recorded;
- After all study procedures have been completed, the subject will be reminded to:
 - Come to the study center for the Day 29 study visit with their first morning urine sample;

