 - Not to take CCX168 medication on the morning of Day 43, unless the visit is scheduled in the afternoon, in which case CCX168 medication should be taken the morning of Day 43; and
 - Continue taking their RAAS blocker(s) at a stable dose, and all their other concomitant medications as usual.

6.8. Study Day 43

The Study Day 43 visit may occur within \pm a 2-day window of the scheduled date. During this visit, the following study procedures will be performed:

- A physical examination (excluding genitourinary, ophthalmic, and female breast assessments) will be performed; body weight and body mass index will be determined;
- Vital signs (temperature, blood pressure, heart rate) will be measured supine after at least 3 minutes of rest;
- Serum pregnancy test for women of childbearing potential;
- Serum chemistry and hematology; an eGFR will be calculated;
- Urinalysis, including pH, specific gravity, glucose, nitrite, ketones, bilirubin, urobilinogen, RBCs, and WBCs on a first morning urine sample collection;
- A plasma sample will be collected for PK assessment; the time of sample collection as well as the date and time of the last dose of CCX168 prior to sample collection will be recorded;
- Any changes in concomitant medication use will be recorded;
- Study drug accountability will be performed on all returned study medication;
- Four bottles of CCX168 study medication will be dispensed to the subject, with dosing instructions;

- The subject will be asked to take the dose of study medication, 3 x 10 mg CCX168 capsules, while at the study center, unless the medication has already been taken that morning; the time of dosing will be recorded;
- All adverse events will be recorded;
- After all study procedures have been completed, the subject will be reminded to:
 - Come to the study center for the Day 57 study visit with their first morning urine sample;
 - Store the study medications in a cool and dry place according to label instructions for the duration of the study;
 - Take the CCX168 medication every morning and evening, approximately 12 hours after the morning dose;
 - Not to take CCX168 medication on the morning of Day 57, unless the visit is scheduled in the afternoon, in which case CCX168 medication should be taken the morning of Day 57; and
 - Continue taking their RAAS blocker(s) at a stable dose, and all their other concomitant medications as usual.

6.9. Study Day 57

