7. STUDY ASSESSMENTS

7.1. Efficacy Assessments

7.1.1. Urinary Protein:Creatinine and Albumin:Creatinine

Proteinuria will be assessed by measuring the protein, albumin, and creatinine concentrations on first morning urinary samples, and calculating the urinary protein:creatinine ratio and urinary albumin:creatinine ratio. Results will be expressed as mg protein/g creatinine or mg albumin/g creatinine. This will be done by the central laboratory.

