7.2.2. Clinical Safety Laboratory Assessments

The following tests will be performed at the visits identified in the [Time and Events Table](#).

- Hematology: hemoglobin, hematocrit, red blood cell (RBC) count, white blood cell (WBC) count with differential, platelet count, mean cell hemoglobin (MCH), mean cell hemoglobin concentration (MCHC), mean corpuscular volume.
- Serum Chemistry: liver panel (bilirubin, lactate dehydrogenase [LDH], SGOT/AST, SGPT/ALT), renal panel (BUN, creatinine), pancreatic enzymes (amylase and lipase), creatine phosphokinase (CPK), albumin, sodium, potassium, magnesium, bicarbonate, chloride, calcium, inorganic phosphorus, glucose, total proteins, alkaline phosphatase, cholesterol, uric acid.

- Urinalysis: At the central laboratory, pH, specific gravity, glucose, nitrite, ketones, bilirubin, urobilinogen, RBC, and WBC tests.
- Virology (measured only at Screening at the local laboratory): hepatitis B surface antigen, hepatitis C antibodies, HIV 1 and 2 antibodies.

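### PCR is not assayed at Day 43, so a proteinuria rise starting on Days 30 to 43 is seen and confirmed 14 days later than it need be

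*Protocol*

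**What the plan says.** Protocol sections 3 and 4.4 and the synopsis take a subject off study drug in two situations: an unexplained eGFR fall of more than 10 mL/min/1.73 m² or more than 20%, or a proteinuria rise of more than 3 g/g from baseline or to above 8 g/g. Each needs a second value two weeks later. For proteinuria the text is "confirmed by repeat after 2 weeks) during the 12-week treatment period, will exit the treatment phase of the study".

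The Time and Events Table row "Urine protein and creatinine assays" is marked in the treatment period at Days 1, 8, 15, 29, 57 and 85, and the Day 43 cell is blank. Section 6.8 (Day 43) agrees. It includes "Serum chemistry and hematology; an eGFR will be calculated" and also "Urinalysis, including pH, specific gravity, glucose, nitrite, ketones, bilirubin, urobilinogen, RBCs, and WBCs on a first morning urine sample collection", but no urinary protein or creatinine. The slope table in SAP 10.7.1 uses the same six PCR days.

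Section 7.1.1 defines the measure: "Proteinuria will be assessed by measuring the protein, albumin, and creatinine concentrations on first morning urinary samples", done by the central laboratory. Section 7.2.2 places the urinalysis there too: "Urinalysis: At the central laboratory, pH, specific gravity, glucose, nitrite". The right kind of sample therefore already goes to the right laboratory at Day 43.

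Footnote 1 of the Time and Events Table sets the windows: "Visit Days 29, 43, 57, and 85 may occur within a +/- 2-day window of the scheduled visit".

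**The concern.** The two halves of one stopping rule are monitored at different intensities in the middle of treatment. Day 43 falls 14 days after Day 29 and 14 days before Day 57, so it suits a two-week repeat. It serves that purpose for eGFR but not for PCR.

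From Day 29 to Day 85 PCR is measured only every 28 days. If proteinuria worsens soon after Day 29, nothing prompts a repeat until Day 57, and the subject stays on a drug that the rule would have stopped. Section 5.9 also bars other IgAN treatment during dosing, so a late exit can delay alternative therapy unless rescue is invoked under 4.4.

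**Working it through.** **Inputs.** PCR days on treatment after Day 1: 8, 15, 29, 57, 85 (Time and Events Table; SAP 10.7.1). Serum creatinine days: the same plus 43 (Time and Events Table; 6.8). Confirmation interval: 14 days (4.4). Last dosing day: 84 (84-day treatment). Windows: ±2 days at Days 29, 43, 57 and 85. The plan states no figure of its own on this point to reproduce.

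**Gaps between assays, counted from Day 1.**
- PCR now: 7, 7, 14, 28, 28 days.
- eGFR now, and PCR with Day 43 added: 7, 7, 14, 14, 14, 28 days.
- Day 29 to Day 57 with windows: 28 ± 4 = 24 to 32 days. Day 29 to Day 43, and Day 43 to Day 57: 14 ± 4 = 10 to 18 days.

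**Detection and confirmation by day of onset.** Assume the rise persists, is seen at the first PCR on or after onset, and is repeated exactly 14 days later, off schedule if needed. Onset can fall on Days 2 to 84, which is 83 days.

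| Onset | Days | Seen / repeated now | Seen / repeated with Day 43 |
|---|---|---|---|
| 2–8 | 7 | 8 / 22 | 8 / 22 |
| 9–15 | 7 | 15 / 29 | 15 / 29 |
| 16–29 | 14 | 29 / 43 (extra assay) | 29 / 43 (routine) |
| 30–43 | 14 | 57 / 71 | 43 / 57 |
| 44–57 | 14 | 57 / 71 | 57 / 71 |
| 58–84 | 27 | 85 / after dosing | 85 / after dosing |

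**Share confirmable during dosing.** 7 + 7 + 14 + 14 + 14 = 56 of 83 (67%), both now and with the added assay.

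**What changes: onset on Days 30 to 43, 14 of 83 onset days (17%).**
- Delay to first detection now: 57 − 43 = 14 to 57 − 30 = 27 days, mean 20.5.
- Delay with Day 43: 43 − 43 = 0 to 43 − 30 = 13 days, mean 6.5.
- Confirmation: Day 57 + 14 = 71 now; Day 43 + 14 = 57 with the assay.
- Dosing days left at confirmation: 84 − 71 = 13 now; 84 − 57 = 27 with the assay. The difference is 14 days. This is an upper limit, because laboratory turnaround, which the documents do not give, comes off it.

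For onset on Days 16 to 29 no dosing days are saved. The Day 43 repeat becomes part of a routine visit and no longer needs a special order.

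**The case against.** The strongest reply is that the rule never says the repeat must fall on a scheduled visit. That stands, and it rules out two stronger readings.

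- A reader might infer that the proteinuria half of the rule cannot be carried out. The documents do not support this: nothing forbids an unscheduled sample, and a PCR can be ordered on the urine already brought at Day 43.
- A reader might count only scheduled visit pairs exactly 14 days apart. PCR then has the pair 15–29 (onset Days 2 to 15, 14 of 83, 17%). With Day 43 it has 15–29, 29–43 and 43–57 (onset Days 2 to 43, 42 of 83, 51%), as eGFR has now. That looks like a threefold gain in coverage, but it measures something the rule does not ask for. With repeats taken as the rule allows, coverage is 56 of 83 either way.

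Other points also carry weight. Day 43 drops the other urinary efficacy markers, IgA/C3 and the PD samples as well, so it looks like a deliberate safety and PK visit. It still includes physical examination, body weight, blood pressure and serum chemistry with albumin and total protein (6.8, 7.2.2), which are indirect signals of a large rise. Investigator withdrawal and rescue discontinuation (4.4) need no confirmation, and the Medical Monitor reviews safety data in near real time (section 3). A Day 43 PCR would also enter by-visit tables and figures while staying out of the primary slope, so the SAP must say how it is handled.

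What survives is narrower. An unscheduled repeat needs a first abnormal PCR to trigger it, and for onset on Days 30 to 43 no PCR is scheduled before Day 57. The safeguards above cannot act on a value that was not measured.

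**Conclusion.** The point holds as a minor safety-monitoring improvement. Adding PCR at Day 43 brings detection and confirmation forward by 14 days for a persistent rise that starts on Days 30 to 43, and makes the repeat of a Day 29 value routine. It does nothing for onset after Day 43 and does not change which rises can be confirmed during dosing.

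The result assumes a rise that persists, visits on their nominal days and a repeat at exactly 14 days. The documents give no rate of such rises. As an illustration only, if 1% to 20% of 20 subjects had one, with onset spread evenly over the 83 days, the expected number who gain is 20 × 0.01 × 14/83 = 0.03 to 20 × 0.20 × 14/83 = 0.67. The case for the change rests on its low cost. The primary analysis is not affected.

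**What to change.** 1. Add urine protein and creatinine assays at Day 43 in the protocol Time and Events Table, section 6.8 and the SAP 5.6 schedule.
2. Add to section 6.7 a reminder to bring first-morning urine to Day 43. Section 6.6 has the equivalent, "Come to the study center for the Day 29 study visit with their first morning urine sample", and 6.8 has one for Day 57, but 6.7 has none although 6.8 needs the sample.
3. State in 4.4 that any qualifying eGFR or PCR value triggers a repeat at 14 days, unscheduled if no visit falls then (for example Day 8 to Day 22, Day 57 to Day 71). Leave the thresholds as they are.
4. Keep the SAP 10.7.1 slope time points unchanged. State that Day 43 PCR appears in the listings, by-visit summaries (10.2.1, 10.7.5), shift tables (10.7.9) and plots, but not in the fitted slopes or the regression lines drawn from them.

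The cost is about 20 assays, one per subject, on urine that 6.8 already specifies, plus short text edits. The downside is one PCR value per subject that the primary slope does not use, and one more chance of an isolated high value, which the two-week confirmation guards against.
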